11.7 Radiotherapy Quality Assurance (QA)

The NCRI Radiotherapy Trials Quality Assurance (RTTQA) group, in collaboration with the EORTC for European sites, will oversee the quality assurance of the SBRT delivered within the trial to ensure the safety and consistency of radiotherapy delivery at participating sites. Prior to inclusion in the trial, individual centres will need to demonstrate they have robust procedures in place to ensure high quality RTTQA planning and delivery guidelines will be met. During recruitment and prior to any repeat SBRT treatment, prospective review will be performed for all patients. The review will assess the

outlining and planning protocol compliance and must be completed before the patient commences treatment. For further information please refer to the HALT Radiotherapy Planning and Delivery Guidelines document.

All data from both UK and European centres will be uploaded via the EORTC RTQA platform. Further information is provided in the HALT Radiotherapy Planning and Delivery Guidelines and in the HALT Trial Guidance Notes.

11.8 Supportive Care and Concomitant Therapies

All medication considered necessary for the patients' welfare and which is not expected to interfere with the evaluation of the treatment may be given at the discretion of the investigator. All concomitant medications (including start/stop dates, dose/frequency, route of administration and indication) must be recorded in the patient's notes, as well as on the appropriate eCRF.

12 Safety Reporting

12.1 Definitions

Adverse Event (AE)

An AE is any untoward medical occurrence in a patient administered a study treatment; the event does not necessarily have a causal relationship with the treatment.

For the purpose of this trial, any detrimental change in the patient's condition subsequent to the start of the trial (i.e. randomisation) and during the follow-up period should be considered as an AE, in the opinion of the Chief Investigator.

Serious Adverse Event (SAE)

An SAE is any untoward medical occurrence that occurs after randomisation and within the following 140 days and:

- results in death,
- is life-threatening
- requires hospitalisation or prolongation of existing inpatients' hospitalisation
- results in persistent or significant disability or incapacity
- is a congenital anomaly or birth defect

For repeat SBRT treatment (where applicable) any untoward medical occurrence that occurs within 90 days of the last fraction of subsequent SBRT and fulfils one of the criteria above should be reported according to serious adverse event reporting timelines.

In addition, any radiotherapy grade \geq 4 events occurring between 140 days and 1 year after randomisation or 90 days and 1 year after any repeat SBRT should be reported according to serious adverse event reporting timelines.

Important adverse events that are not immediately life-threatening or do not result in death or hospitalisation but may jeopardise the subject or may require intervention to prevent one of the other outcomes listed in the definition above, may also be considered serious.

Progression of the indicated disease and death due to progression of the indicated disease are not considered SAEs.

Pregnancy or aid in the conception of a child whilst participating in a trial is not itself considered an SAE but should be followed up for congenital anomalies or birth defects.

Serious Adverse Reaction (SAR)

A serious adverse reaction is an SAE that is suspected as having a causal relationship to the SBRT treatment, as assessed by the investigator responsible for the care of the patient. A suspected causal relationship is defined as possibly, probably or definitely related (see definitions of causality table).

ity
Description
There is no evidence of any causal relationship with the trial treatment
There is little evidence to suggest there is a causal relationship (e.g. the event
did not occur within a reasonable time after administration of the trial
treatment). There is another reasonable explanation for the event (e.g. the
patient's clinical condition, other concomitant treatment)
There is some evidence to suggest a causal relationship (e.g. because the event
occurs within a reasonable time after administration of the trial treatment).
However, the influence of other factors may have contributed to the event (e.g.
the patient's clinical condition, other concomitant treatments)
There is evidence to suggest a causal relationship, and the influence of other
factors is unlikely
There is clear evidence to suggest a causal relationship, and other possible
contributing factors can be ruled out
There is insufficient or incomplete evidence to make a clinical judgement of the
causal relationship.

Definitions of causality

Related Unexpected Serious Adverse Event

An adverse event that meets the definition of serious and is assessed by the CI or nominative representative as:

- "Related" that is, it resulted from administration of any of the research procedures, and
- "Unexpected" that is, the type of event is not listed in the protocol as an expected occurrence (see Appendix 6)

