11.1 Continuation or interruption of background TKI during SBRT course

Current uncertainty exists regarding the safety of concomitant use of TKI during SBRT treatment. Whilst a break in background TKI therapy whilst receiving SBRT treatment is aimed at minimising the risk of radiation toxicity associated with simultaneous administration of SBRT and TKI, the risk of disease flare whilst off TKI is also a considerable concern. A survey of UK and European oncologists conducted as part of the development of HALT indicated no consensus of opinion as to the best approach. Centres participating in HALT will therefore be given the option to either continue background TKI treatment alongside SBRT or stop TKI treatment during SBRT (with a minimum break of one day before the first SBRT fraction and one day after delivery of the last fraction).

Prior to commencing recruitment for the trial all centres must indicate their chosen policy as to whether they opt for a break in TKI therapy for all patients randomised to receive SBRT or whether they opt to continue administration of TKI during SBRT for all patients randomised to receive SBRT. For centres opting to interrupt TKI therapy during SBRT treatment patients must stop TKI at least one day prior to the first dose of SBRT and re-commence no earlier than one day after the last dose of SBRT. For centres opting to continue TKI therapy during SBRT treatment no changes to dose or frequency of TKI therapy is required.

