12.2 Reporting Adverse Events to ICR-CTSU

For non-UK reporting requirements please see Appendix A7

Any toxicity, sign or symptom that occurs after randomisation which is not unequivocally due to progression of disease, should be considered an AE.

All AEs must be reported on the relevant electronic CRF and submitted to ICR-CTSU.

• Toxicity evaluation

The National Cancer Institute Common Terminology Criteria for Adverse Events (CTCAE) version 4 scoring criteria will be used for all toxicity assessments for patients randomised to both the treatment (SBRT) and control groups.

The severity of AEs should be graded according to the appropriate CTCAE criteria. For each AE, the highest grade observed since the last visit should be reported.

Whenever one or more toxicity/sign/symptom corresponds to a disease or a well-defined syndrome, only the main disease/syndrome should be reported.

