13.4 Interim Analyses and Stopping Rules

The TSC will monitor recruitment rate and may recommend trial closure if it is significantly lower than expected and continuation of the trial is deemed futile.

A futility analysis will be conducted after 50% of the PFS events have been recorded (49 PFS events, ~70 patients recruited). If the HR >1.0 then treatment with SBRT will be deemed futile. This analysis will contribute to the decision for continuation to phase III.

The IDMC will review emerging safety data. This will include a formal safety review after 10 patients recruited to SBRT given concurrently with background TKI have completed the 3 month follow-up visit to assess the impact of concurrent background TKI on radiotherapy toxicity and after 10 patients recruited to SBRT given sequentially with the background TKI have completed the 3 month follow-up visit to assess disease flare (defined as disease progression occurring between stopping background TKI and restarting background TKI following completion of (initial) SBRT treatment).

In all patients randomised to SBRT, consideration will be given to stopping the trial should the rate of grade 4/5 acute radiotherapy-related toxicity (defined as within 90 days of last treatment administration, including repeat SBRT treatment as applicable) be unacceptable (to be agreed by the TMG and IDMC a priori).

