	procedure/process can be identified to be a significant cause of non-	
	compliance, the trial can be adapted to increase compliance rates	
Safety	Grade 4/5 acute SBRT-related toxicity incidence and acceptability as	
	determined by the IDMC	
	Acceptable patient toxicity levels at centres where SBRT given	
	concurrently with background TKI, as assessed by the IDMC	
	Acceptable disease flare cases at centres treating patients sequentially	
	with SBRT followed by background TKI as assessed by the IDMC	

The independent HALT Trial Steering Committee will use the information obtained by the feasibility assessment including any advice and recommendations from the IDMC to guide its decision as to whether progression to a phase III trial should proceed.

If the HALT TSC determine the criteria have not be reached to a sufficient degree and advise against proceeding to a phase III the phase II trial will proceed to its conclusion as detailed in this protocol. Proposed actions for of transition to phase III.

If the decision to proceed to the phase III is made, additional funding will be required to support the development and conduct of the trial. The interim analysis planned during the phase II is intended to occur at a timepoint that allows a sufficient period of time to apply and obtain funding whilst allowing

recruitment to continue ahead of the phase III trial. A period of 12 months from interim analysis to funding confirmation is anticipated to allow sufficient time to apply and obtain funding. Recruitment will continue to the phase II trial during this period and it is possible that accrual will continue past the phase II required sample size depending on the rate of recruitment and timeframe for funding confirmation (given the constraints of funding application deadlines).

i) *Funding is confirmed for the phase III trial* - Following confirmation of funding a 6 month period is anticipated to allow for the appropriate approvals and documentation to be put in place prior to commencing the phase III trial. The seamless transition from phase II to phase III will allow recruitment to continue during this period with patients contributing to the phase III trial.

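### A serious or fatal disease flare during the TKI break has no SAE route, because flare is defined as progression and progression is exempt from SAE reporting

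*Protocol*

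**What the plan says.** Section 11.1 of the protocol lets each centre either continue the TKI through SBRT or interrupt it, with at least one day off before the first fraction and one day off after the last. It says of the interruption that "the risk of disease flare whilst off TKI is also a considerable concern".

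Section 13.4 provides a formal IDMC safety review of flare once 10 patients treated sequentially have completed the 3 month follow-up visit. Flare is "defined as disease progression occurring between stopping background TKI and restarting background TKI following completion of (initial) SBRT treatment".

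Appendix A1 lists, among the safety items for the transition, "Acceptable disease flare cases at centres treating patients sequentially", as judged by the IDMC. With recruitment, futility, compliance and other safety items, it informs the TSC and is used to "guide its decision as to whether progression to a phase III trial should proceed".

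On reporting:
- **12.1, SAE definition:** "Progression of the indicated disease and death due to progression of the indicated disease are not considered SAEs". No exception is made for flare.
- **12.1, AE definition:** a detrimental change "subsequent to the start of the trial (i.e. randomisation) and during the follow-up period should be considered as an AE", in the Chief Investigator's opinion.
- **12.2:** a toxicity, sign or symptom after randomisation "which is not unequivocally due to progression of disease, should be considered an AE".
- **12.3:** SAEs go to the trials unit within 24 hours, with the site's causality assessment.
- **12.4:** the Chief Investigator assesses SAEs reported as related to the study treatment, which is specified as SBRT.

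**The concern.** Exempting progression from SAE reporting is ordinary practice when progression is simply the course of the disease. In the off-TKI window the protocol itself treats it as something else: a possible consequence of an interruption made in order to give trial treatment, serious enough for its own IDMC review. The same event is a safety outcome in 13.4 and Appendix A1 and, by 12.1, not a serious adverse event.

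What is at stake is speed and causal assessment. If the first patient at an interrupting centre is admitted or dies from flare, nothing in section 12 requires the site to tell the trials unit within 24 hours, and nobody is asked whether the interruption contributed.

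**Working it through.** The point rests on no sample size, power or alpha figure, so there is no plan figure to reproduce. The check sets the rules side by side.

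1. **The chain.** Flare is progression (13.4). Progression, and death from it, is not an SAE (12.1). Only SAEs travel by 12.3, and only SAEs are assessed under 12.4. So an event the site judges to be flare enters neither.

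2. **Is the time window the obstacle?** No. The SAE window runs 140 days from randomisation and SBRT should start within 4 weeks (28 days), which leaves 140 − 28 = 112 days. Course length sits in the radiotherapy guidelines, which are not shown. Assuming course and break take less than 112 days, the initial break lies inside the SAE window. The progression exemption alone removes the event.

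3. **The other TKI policy.** Serious toxicity under concurrent TKI is an SAE and is reported within 24 hours (12.3). The IDMC is asked to judge both policies (13.4, Appendix A1), but only one policy's characteristic harm has a prompt route.

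4. **What the other routes deliver.**
   - *Efficacy data (4.1).* Every death is a PFS event and is captured. Progression in five or fewer SBRT-suitable extracranial lesions is not a PFS event, and symptomatic progression counts only if it needs palliative tumour-specific intervention. An admission that settles once the TKI restarts may therefore not register as an event.
   - *Visits (10.3, 10.7).* The first scheduled assessment is at 8 weeks. The rule for progression suspected between visits is worded for the 3 monthly visits. Whether onset fell inside the break may have to be reconstructed.
   - *Treatment dates (11.8) and patient status (10.4).* These go on the eCRF, but the protocol does not say that they are to be linked to progression in order to identify flare.
   - *IDMC review (13.4).* It waits for the tenth sequential patient's 3 month visit. The schedule in 10.7 places the first 3 monthly visit at 5 months after randomisation.

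5. **Repeat SBRT.** The flare definition is confined to the initial course. The toxicity stopping rule in the same section expressly includes repeat SBRT. A serious flare in a break for a repeat course falls outside both the SAE rule and the flare definition.

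6. **The AE rules.** Section 12.1 counts any detrimental change, with no exclusion for progression. Section 12.2 leaves out what is unequivocally due to progression. The two sections give different answers for the same event.

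7. **Would an SAE form suffice?** Not fully. Review under 12.4 is triggered by relatedness to SBRT. The definition of a related unexpected SAE in 12.1 refers more widely to any research procedure. A flare attributed to the TKI break would not clearly qualify for 12.4 even if reported.

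Context only: the protocol gives no flare rate, so take a range. The chance that a 10-patient review contains at least one flare is 1 − (1 − p)^10, which is 40% at p = 5%, 65% at 10%, 89% at 20% and 97% at 30%. With zero flares in 10, the one-sided 95% upper limit is 1 − 0.05^(1/10) = 26%. These figures assume complete capture. They describe the review and do not measure the effect of the SAE rule.

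**The case against.** The best reply is that an event which is not an SAE can still be known to the trial. Deaths are PFS events. Progression is assessed at each visit or sooner if clinically indicated, and scans showing it are uploaded. Status is followed to death, and medication dates are on the eCRF. The IDMC's flare review is defined by progression, not by SAE forms. The eCRF and the IDMC charter are not shown and may contain a flare item. An investigator who doubts that an admission is due to progression can still report it.

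Most of this stands, and it rules out several stronger readings:
- *Flare is not reported at all, or the IDMC judges data from which serious cases were removed.* The protocol does not say that the IDMC's count is limited to section 12 reports.
- *Flare is exempt from AE reporting.* Section 12.2 excludes only what is unequivocally due to progression, and the AE definition in 12.1 excludes nothing on that ground.
- *Flare is a go/no-go criterion.* It is one of several items, without a numeric limit, that guide the TSC.
- *One missed case turns 1/10 into 0/10.* That would require a serious flare to be invisible without an SAE form, which the protocol does not support.

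The reply does not restore a prompt route or a causality question for an event the site does attribute to progression. The remaining routes are later or partial, and an unseen form would not change the rule in 12.1 that sites are told to follow.

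**Conclusion.** The point holds as a gap in expedited safety reporting. A hospitalisation or death judged to be flare in the off-TKI window has no 24-hour SAE route and no causality review, although the protocol names flare as a safety outcome and uses it in the transition assessment. Repeat-course breaks are covered least, and the AE rules in 12.1 and 12.2 need reconciling.

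Its practical size depends on the true flare rate, the number of interrupting centres and what the eCRF captures, none of which is given. The conclusion assumes that sites apply 12.1 literally and that centres choosing interruption also interrupt for repeat courses, as 11.1 reads but does not say outright. It implies no view on which TKI policy is preferable. The change is worth making because a stated rule, and not a missing detail, produces the gap, and closing it is cheap.

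**What to change.** Reconcile 12.1 to 12.4, 13.4 and Appendix A1 on how flare is reported and how it reaches the IDMC:

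- **12.1 and 12.3:** state that the progression exemption does not apply to an event meeting a seriousness criterion with onset between stopping the TKI for SBRT, initial or repeat, and restarting it. Report it on the existing SAE form, flagged as possible flare.
- **12.4:** extend the Chief Investigator's review to events possibly related to the TKI interruption, and align this with the wider notion of relatedness in 12.1.
- **12.1 and 12.2:** give one AE rule for progression.
- **13.4 and Appendix A1:** tabulate the flagged events for the IDMC, and say whether repeat-course breaks count as flare.
- **Appendix A6:** state whether flare is expected. It is not listed, so a flare judged related would trigger the 15-day reporting in 12.5.

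The cost is a few sentences, a tick box and a few extra SAE reports, some of which will turn out to be natural progression. No procedure is added, and neither TKI policy changes.

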12.2 Reporting Adverse Events to ICR-CTSU

For non-UK reporting requirements please see Appendix A7

Any toxicity, sign or symptom that occurs after randomisation which is not unequivocally due to progression of disease, should be considered an AE.

All AEs must be reported on the relevant electronic CRF and submitted to ICR-CTSU.

• Toxicity evaluation

The National Cancer Institute Common Terminology Criteria for Adverse Events (CTCAE) version 4 scoring criteria will be used for all toxicity assessments for patients randomised to both the treatment (SBRT) and control groups.

The severity of AEs should be graded according to the appropriate CTCAE criteria. For each AE, the highest grade observed since the last visit should be reported.

Whenever one or more toxicity/sign/symptom corresponds to a disease or a well-defined syndrome, only the main disease/syndrome should be reported.

12.3 Reporting of Serious Adverse Events to ICR-CTSU

Any SAE that occurs following randomisation and up to 140 days post randomisation must be reported. All SAEs occurring up to 90 days post subsequent SBRT (treatment group only, where applicable) must be reported. As detailed above, radiotherapy related SAEs occurring > 140 days post randomisation (or > 90 days post subsequent SBRT) and at 1 year following last dose of radiotherapy treatment (for SBRT arm only) should also be reported.

All SAEs should be reported to ICR-CTSU within 24 hours of the Principal Investigator (or designated representative) becoming aware of the event, by completing the HALT SAE form and emailing to:

The ICR-CTSU safety desk Email address: [contact] For the attention of the HALT Trial team

As much information as possible, including the Principal Investigator's assessment of causality, must be reported to ICR-CTSU in the first instance. Additional follow up information should be reported as soon as it is available.

All SAE forms must be completed signed and dated by the Principal Investigator or designated representative.

12.4 Review of Serious Adverse Events

The Chief Investigator (or designated representative) will assess all SAEs reported as related to the study treatment, which for the purposes of this trial will be SBRT, for causality and expectedness (NB. The Chief Investigator cannot down-grade the Principal Investigator's assessment of causality.)

SAEs assessed as having a causal relationship to study treatment and as being unexpected will undergo expedited reporting to the relevant authorities and all other interested parties by ICR-CTSU (see 12.5). Sites should respond as soon as possible to requests from the Chief Investigator or designated representative (via ICR-CTSU) for further information that may be required for final assessment of an SAE.

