12.5 Expedited Reporting of Related Unexpected SAEs

If an SAE is identified as being related and unexpected by the Chief Investigator it will be reported by ICR-CTSU to the main REC, the Sponsor and all other interested parties within 15 days of being notified of the event.

The Principal Investigators at all actively recruiting sites will be informed of any related unexpected SAEs occurring within the trial at appropriate intervals.

The collaborative group in each participating country will report related unexpected SAEs as per their local requirements to IECs and local investigators.

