- Rectal Haemorrhage
- Haematuria
- Urinary frequency
- Urinary incontinence
- Urinary retention
- Urinary urgency

General

- Fever
- Fatigue
- Myelitis

Dermatology/Skin

- Dermatitis
- Hair loss (to treatment area)

Related to fiducial marker insertion

- Bleeding
- Sepsis (urinary and systemic)
- Pneumothorax

A7. Non-UK safety reporting requirements

The site Principal Investigator or designee is responsible for reporting SAEs to the ICR-CTSU as per the protocol.

[figure not shown]
The EORTC will report related unexpected SAEs as per national requirements to IECs and local investigators.

Further Sponsor safety reporting notification requirements will be agreed in the international site agreements.

HALT Protocol

ICR-CTSU

A8. Translational study collection (6 sampling points per patient)

GL DNA = Germ Line DNA (collected in EDTA tube)

cfDNA = circulating free tumour DNA (Streck tube)

RNA = RNA for analysis of T cell Repertoire from peripheral blood (1 x Tempus[™] blood RNA tube – 3ml blood draw)

FFPE Research Block: When available additional cores from biopsy of oligoprogressive lesions should be placed in a separate pot for fixation in FFPE at baseline and at the time of progression if biopsy was clinically indicated. Clinical diagnostic requirements take precedence.

HALT Protocol

ICR-CTSU

A9. GLOSSARY

AE	Adverse Event
ALT	Alanine Aminotransferase
ANC	Absolute Neutrophil Count
AST	Aspartate Aminotransferase
AUC	Area Under Curve
CI	Chief Investigator
CIS	Carcinoma In Situ
CRF	Case Report Form
DCF	Data Capture Form
DFS	Disease Free Survival
eCRF	Electronic Case Report Form
ECOG	Eastern Cooperative Oncology Group
EORTC	European Organisation for Research and Treatment of Cancer
FBC	Full Blood Count
G-CSF	Growth Colony-Stimulating Factors
GFR	Glomerular Filtration Rate
HR	Hazard Ratio
IB	Investigator's Brochure
ICR	The Institute Of Cancer Research
IDMC	Independent Data Monitoring Committee
LFT	Liver Function Test
MDT	Multi-disciplinary team
MRC	Medical Research Council
NCI CTCAE	National Cancer Institute Common Terminology Criteria for Adverse Events
OAR	Organs At Risk
PI	Principal Investigator
PIS	Patient Information Sheet
QoL	Quality of Life
R&D	Research and Development
RCT	Randomised controlled trial
RTTQA	NCRI Radiotherapy Trials Quality Assurance
SAE	Serious Adverse Event
SAR	Serious Adverse Reaction
SBRT	Stereotactic Body Radiotherapy
SMPC	Summary of Product Characteristics
SUSAR	Suspected Unexpected Serious Adverse Reaction

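### Section 12.1 counts harm from any research procedure as related, but the SAR definition, the causality scale and section 12.4 look only to SBRT or the trial treatment, so a serious fiducial-insertion event may miss Chief Investigator assessment and expedited reporting

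*Protocol*

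**What the plan says.** The protocol describes relatedness in several places, with two different scopes.

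- Section 12.1, Related Unexpected Serious Adverse Event: the event is related if "it resulted from administration of any of the research procedures". It is unexpected if its type is not listed as expected in Appendix 6.
- Section 12.1, Serious Adverse Reaction: "A serious adverse reaction is an SAE that is suspected as having a causal relationship to the SBRT treatment", as judged by the investigator caring for the patient.
- Section 12.1, causality table: the categories are worded around the trial treatment. The lowest reads "There is no evidence of any causal relationship with the trial treatment".
- Section 12.4: the Chief Investigator "will assess all SAEs reported as related to the study treatment, which for the purposes of this trial will be SBRT", for causality and expectedness. Then "SAEs assessed as having a causal relationship to study treatment and as being unexpected will undergo expedited reporting".
- Section 12.5: "If an SAE is identified as being related and unexpected by the Chief Investigator it will be reported by ICR-CTSU", within 15 days. The restriction to SBRT is not repeated here.

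Section 11.2 provides for fiducial marker insertion as preparation for SBRT, with appointments booked before randomisation. Appendix A6 gives it a heading of its own, "Related to fiducial marker insertion", covering bleeding, sepsis and pneumothorax. That heading sits inside a list headed SBRT group. A6 treats its listed events as expected, and exempt from SAE reporting, only at grade 2 or lower.

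**The concern.** Sections 12.4 and 12.5 should carry out the definition of a related unexpected SAE in 12.1. Section 12.4 is narrower than that definition, and it is the only step the protocol describes between receipt of an SAE and a judgement on causality and expectedness. A site that uses the causality scale as worded is asked about the trial treatment, not about research procedures. If it attributes an event to a procedure and not to SBRT, it has grounds to report the event as unrelated, and 12.4 does not then send it to the Chief Investigator.

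At stake is the handling of individual cases. Expedited reporting exists for rare serious events, so the expected rarity of these events does not settle the matter. Some will be harms of a procedure done only so that trial SBRT can be given. If sites read the scope differently, the set of events assessed will depend on local interpretation.

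**Working it through.** No arithmetic applies. The check compares the passages and follows one event through them.

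**Scope of relatedness**

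| Place | Scope |
|---|---|
| 12.1, Related Unexpected SAE | any research procedure |
| 12.1, Serious Adverse Reaction | SBRT |
| 12.1, causality table | trial treatment |
| 12.4, Chief Investigator assessment | study treatment, stated to be SBRT |
| 12.4, expediting | study treatment |
| 12.5, expediting | not restated; acts on what the Chief Investigator has identified |

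**One event followed through.** Take a patient allocated to SBRT who has a pneumothorax of grade 3 or higher, with hospital admission, after fiducial insertion and before the first fraction.

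1. *Is it an SAE?* Under 12.1, yes, if it occurs after randomisation and within 140 days. Section 11.2 asks for the appointment to be booked before randomisation. I take the insertion itself to follow allocation, since control patients receive no SBRT.
2. *Does it reach the trials unit?* Yes. Section 12.3 requires every SAE in the window to be sent within 24 hours, whatever its cause.
3. *Is it related under the wide definition?* Yes, if insertion for trial SBRT counts as a research procedure.
4. *Is it expected?* A6 lists pneumothorax only at grade 2 or lower, so at grade 3 or higher it falls outside that list.
5. *Is it related under the narrow wording?* No SBRT has been given, so a site answering literally can say it is not related to SBRT.
6. *Does 12.4 send it to the Chief Investigator?* Not on that answer. Section 12.5 is not narrower, but it acts only on SAEs the Chief Investigator has identified as related and unexpected.

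Steps 3 and 4 make the event reportable within 15 days under 12.1 and 12.5. Steps 5 and 6 leave it without a stated route there. Another site could treat insertion as part of SBRT, relying on A6's SBRT group heading, and the same event would then be assessed.

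**A qualification on step 4.** Section 12.1 speaks of the type of event, whereas A6 adds a grade limit. On a reading by type alone, the three listed complications would be expected at any grade. A serious insertion complication of any other type would be unexpected on either reading, so the mismatch of scope does not depend on this.

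**The case against.** The strongest reply is that this is loose wording with safeguards around it. Section 12.4 says which SAEs the Chief Investigator will assess; it does not say that no others may be assessed. Every SAE to 140 days reaches the trials unit with the Principal Investigator's causality judgement. Section 12.5 leaves out the SBRT limit, so the wide definition can apply once an event is before the Chief Investigator. The IDMC reviews emerging safety data under 13.4. A6 lists fiducial events under SBRT group, which suggests that insertion was meant to count as part of SBRT.

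Much of this stands. A reader might infer that procedure-related harm never reaches the Chief Investigator or expedited reporting; the text does not support that, and the most that can be said is that it may not. The safeguards still leave the step between receipt and assessment described for SBRT-related events only, and the A6 heading is an inference that 12.4 does not state.

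Three other strong readings also fail.

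- *The TKI break.* Section 11.1 says that at interrupting centres "patients must stop TKI at least one day prior to the first dose of SBRT", and one might place its harms in this gap. The harm the protocol names is disease flare, defined in 13.4 as progression. Section 12.1 excludes progression from SAEs, and 13.4 gives flare its own IDMC review, so 12.4 is not what keeps it out of expedited reporting.
- *Biopsies.* They are voluntary and requested without regard to allocation, so they are not an SBRT-arm procedure.
- *Understated harm in the treatment comparison.* Section 12.2 collects all adverse events after randomisation in both groups, and 13.3 provides for comparison between them. The mismatch affects case assessment and expediting, not data collection.

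**Conclusion.** The protocol is wrong as written, within narrow limits: the definition of a related unexpected SAE and the provisions that act on it have different scopes and must be reconciled. The consequence is that an unexpected SAE which a site attributes to a research procedure other than SBRT may miss Chief Investigator assessment and 15-day reporting, and that sites may classify the same event differently.

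The size cannot be stated as a number. Section 5.1 anticipates 73 patients in the SBRT group, but no document gives the share having fiducials or the rate of serious complications. The worked example rests on three assumptions: that insertion for trial SBRT is a research procedure, that it takes place after randomisation, and that A6's grade limit is part of what makes an event expected. The difference in scope rests on none of them.

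A reader might also infer that the stopping consideration in 13.4 is faulty because it counts only radiotherapy-related toxicity. That is a separate design choice, with an acceptability limit to be agreed by the TMG and IDMC, and this inconsistency does not show it to be wrong.

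**What to change.** Use the wide scope of 12.1 throughout. In the Serious Adverse Reaction definition, the causality table and section 12.4 (both the assessment sentence and the expediting sentence), refer to SBRT or any other research procedure. State that fiducial insertion for trial SBRT is included. Add a field to the SAE form recording which element is suspected. Section 12.5 can stay as it is once 12.4 agrees with 12.1.

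Wording limited to procedures required by allocation to SBRT would not be enough. It would leave out research procedures in the control group, such as the mandatory blood samples, and would still not match 12.1.

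The cost is a wording amendment, one field on a form and a few more SAEs for the Chief Investigator to assess. Treatment, sample size and the efficacy analysis do not change.
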